## 7.3 Multiple Comparison and Two-Stage Design

The gatekeeping procedure will be applied to protect the overall type-I error rate due to the multi-dose active treatments vs the placebo comparisons. Specifically, the HD group will be compared to the placebo group first for the primary efficacy endpoint with  $\alpha=0.05$ . If p-value is  $<0.05$ , then the LD group will be compared to placebo for the primary efficacy endpoint also with  $\alpha=0.05$ . If the HD group is not statistically significant in the first comparison, the LD group will automatically be considered not significant for the primary efficacy endpoint.

The study will potentially be carried out in two stages. The first stage (Stage 1) will enroll approximately 20 subjects per treatment group for a total of 60 subjects. After these first 60 subjects have completed the efficacy assessments through Day 30, an interim analysis will be conducted to compare the primary efficacy endpoints between each active dose group against placebo.

- If a significant difference ( $p \leq 0.05$ ) in the primary endpoint is observed between the active treatment and placebo groups, the study will be stopped unless further enrollment is needed to provide additional evidence in support of the secondary endpoints.

- If a significant difference ( $p \leq 0.05$ ) in the primary endpoint is not observed between the active treatment and placebo groups, enrollment will proceed to Stage 2 for another 20 patients per group
- If one of the active dose groups is dropped, the remaining active dose and placebo groups will continue into Stage 2 for another 30 subjects per treatment group.
- The Stage 2 population may be adapted based on the AKI risk factor distribution in the interim analysis population, which includes but is not limited to the following:
  - Estimated glomerular filtration rate (eGFR)  $\geq 20$  and  $< 30$  mL/min/1.73m^2 \*\*
  - Estimated glomerular filtration rate (eGFR)  $\geq 30$  and  $< 60$  mL/min/1.73m^2
  - Age  $\geq 65$  years
  - Combined valve and coronary surgery
  - Previous cardiac surgery with sternotomy
  - Documented New York Heart Association Class III or IV within 1 year prior to surgery
  - Left ventricular ejection fraction  $\leq 35\%$
  - Congestive heart failure
  - Diabetes mellitus requiring insulin
  - Type 2 diabetes mellitus with albuminuria (urine albumin  $> 300$  mg/g of creatinine as documented in medical history)
  - Current inpatient status for management of cardiac or pulmonary disease
  - Preoperative anemia (hemoglobin  $< 10$  g/dL upon Screening)

\*\* Condition eGFR  $\geq 20$  and  $< 30$  is taken as 2 counts. All other conditions listed above are taken as 1 count.

Note that in this study, the composite preconditioning biomarkers are being measured for the first time in cardiac surgery patients treated with the study medication. Because of the multi-dimensional data and lack of prior knowledge, it is not possible to plan all potential adaptations upfront. Therefore, the above adaptation rule will only serve as a guidance. As such, no type-I error will be adjusted for the potential 2-stage design and analysis.

If enrollment for Stage 2 is adapted based on AKI risk factors, subjects in Stage 2 will be analyzed separately from subjects in Stage 1. If so, Stage 1 and Stage 2 can be viewed as two separate studies. Hence, the Stage 2 analysis will independently use the gatekeeping procedure with the same 2-sided  $\alpha = 0.05$ . If there are enough high-risk subjects in Stage 1 (eg,  $N \geq 5$ /group), the high-risk Stage 1 subjects may be pooled with Stage 2 subjects as a secondary analysis.

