### 7.5.1 Primary Efficacy Endpoint Analysis

The primary efficacy endpoint (geometric mean of the ratios of maximum PreOp over baseline in preconditioning biomarkers, Section 5.1) will be summarized using descriptive statistics (N, mean, median, standard deviation, minimum, and maximum) in the log scale and presented after the anti-log (exponential) transformation for each group separately.

An analysis of covariance (ANCOVA) model will be applied to the log-transformed primary efficacy endpoint. The model will include treatment group as main effect, and surgery type and time on-pump as covariates. Least squares mean (LSM) and the 95% confidence interval (CI) will be calculated for each treatment group and for the between active treatment and placebo difference. The LSM (95% CI) will be anti-log transformed and presented as the geometric LSM (GLSM) and 95% CI for each treatment group, and GLSM ratio (and 95% CIs) for each active treatment over placebo.

A sensitivity analysis will be carried out by the Cochran-Mantel-Haenszel (CMH)  $\chi^2$  test for the row mean score difference between active treatment and placebo stratified by the surgery type and time on pump. A modified ridit score will be used in the calculation of the CMH test statistic. As a supplementary analysis for the primary endpoint, each component of the composite endpoint

- $\frac{\text{max PreOp HO-1}}{\text{Baseline HO-1}}$
- $\frac{\text{max PreOp ferritin}}{\text{Baseline ferritin}}$
- $\frac{\text{max PreOp IL-10}}{\text{Baseline IL-10}}$

will be analyzed in the same way as for the primary efficacy endpoint.

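### If a dose is dropped and the two stages are pooled, the primary model has no stage term and compares that dose with a placebo arm that is 60% non-concurrent

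*SAP*

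**What the plan says.** SAP 7.3 describes a possible two-stage trial. On Stage 1: "The first stage (Stage 1) will enroll approximately 20 subjects per treatment group for a total of 60 subjects". If the interim shows no significant difference, "enrollment will proceed to Stage 2 for another 20 patients per group". On a dropped dose: "If one of the active dose groups is dropped, the remaining active dose and placebo groups will continue into Stage 2", with 30 more subjects in each of those two groups.

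One sentence governs how the stages are kept apart: "If enrollment for Stage 2 is adapted based on AKI risk factors, subjects in Stage 2 will be analyzed separately from subjects in Stage 1". No sentence covers a Stage 2 that is not adapted in that way.

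For the primary endpoint, SAP 7.5.1 specifies an ANCOVA on the log scale: "The model will include treatment group as main effect, and surgery type and time on-pump as covariates". It reports each active dose against placebo. SAP 7.5.2.1 analyses the tubular-injury composite similarly. Neither section names stage, calendar time or a restriction to concurrent controls. SAP 7.5 allows other covariates after blinded review and gives AKI risk factor and site as examples.

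**The concern.** Randomisation protects a comparison between subjects who could have been assigned to either arm. Once a dose closes, later placebo subjects could no longer have received it. Pooling them into that dose's control adds any change over time to the treatment difference.

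Such change is plausible. SAP Appendix B records that the pre-operative biomarker window widened from 1 to 4 hours and that the Day 1 post-operative sampling columns were reduced. This is not an error, and the documents do not say whether the change fell between stages. It does show that sampling practice can move during a trial, and surgery type and pump time would not adjust for it.

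At stake are the dropped dose's estimate, confidence interval and p-value. If the high dose is the one dropped, that contrast also comes first in the gatekeeping order.

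**Working it through.** **Inputs from the SAP.**
- Stage 1: about 20 per arm. Stage 2 after a drop: 30 placebo, 30 retained dose, 0 dropped dose (7.3).
- Two-sided alpha 0.05 (7.2).
- Primary log composite, mean (SD): high dose 1.30 (0.56), low dose 1.07 (0.52), placebo 0.19 (0.19). Secondary log composite: SD 0.51, difference 0.4 (7.1).

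**Assumptions.** The stages are pooled, the dropped dose stops at about 20 subjects, and drift is additive on the log scale. The size of the drift is not in the documents.

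**The plan's own figures.** SAP 7.1 states 40%, 69% and 86% power for the secondary composite at 10, 20 and 30 per group. A normal approximation gives 41.8%, 69.9% and 85.9%; the noncentral t gives 38.2%, 67.6% and 84.8%. These agree to within about 2 points, so SD 0.51 and difference 0.4 are taken as read.

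**Non-concurrent share.** 30/(20 + 30) = 60% of pooled placebo.

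**Bias.** With a Stage 2 shift d, the pooled placebo mean moves by (30/50)d and the dropped-dose mean does not move. Bias of dropped dose minus placebo = −0.6d. The retained dose is also 20 + 30, so its shift cancels. With no drop, every arm is 20 + 20 and all contrasts cancel.

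**Standard errors** (SD units, other covariates ignored).
- Pooled, no stage term: √(1/20 + 1/50) = √0.070 = 0.265.
- With stage: the stage effect is estimated within the two continuing arms, with variance 1/[2 × (20 × 30/50)] = 1/24. The contrast variance is 1/20 + 1/50 + 0.6²/24 = 0.085, giving 0.292.
- Stage 1 only, 20 v 20: √(1/20 + 1/20) = 0.316.

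**Type I error of the dropped-dose contrast** (20,000 simulated trials per case; equal variances, no treatment effect, same drift in both continuing arms; surgery type, pump time and the decision to drop not modelled).

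| Drift (SD) | Bias (SD) | No stage term | With stage term |
|---|---|---|---|
| 0 | 0 | 5% | about 5% |
| 0.2 | −0.12 | 7% | about 5% |
| 0.3 | −0.18 | 10% | about 5% |
| 0.5 | −0.30 | 19% | about 5% |

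**Scale against the planned effects.** At SD 0.51, a drift of 0.5 SD is 0.255 log units and the bias is 0.6 × 0.255 = 0.153. That is 0.153/1.11 = 14% and 0.153/0.88 = 17% of the planned primary differences (1.30 − 0.19 and 1.07 − 0.19), but 0.153/0.4 = 38% of the secondary one.

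**Limits of the stage term.**
- With SDs of 0.19, 0.52 and 0.56 for placebo, retained and dropped arms, rejection is 8.6% at zero drift without stage, and about 7.5% to 8% with stage at every drift tried (0 to 0.4 log units). That excess comes from unequal variances.
- If only placebo drifts, the estimated stage effect is d/2 and half the bias remains: −0.6d + 0.6(d/2) = −0.3d. Rejection is then about 7.6% at 0.5 SD.

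**The case against.** The strongest objection is that pooling is inferred from silence. The SAP never says an unadapted Stage 2 is pooled, its abbreviation list includes an inverse-normal p-value method that the methods text does not use, and SAP 7.3 calls the adaptation rule guidance only. This stands. The documents do not support reading the SAP as committed to a biased comparison; the documented gap is a missing combination rule.

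The branch is also narrow. It needs a second stage, a dropped dose, no risk-based adaptation, and pooling. The protocol plans about 42 per group at 1:1:1 with no stages, close to the no-drop branch (20 + 20), where the problem cannot arise. That lowers the likelihood. However, SAP section 1 says the SAP supersedes the protocol, and the drop branch is still in its text.

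A reader might infer that any drift passes straight into the estimate. It does not. Case mix carried by surgery type or pump time is adjusted out, and a proportional assay shift affecting both of a subject's samples cancels in the ratio to baseline. The option to add covariates after blinded review could admit stage, but does not name it.

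A reader might also extend the table to 0.8 SD, where type I error reaches 39%. That drift is 0.8 × 0.51 = 0.41 log units, about twice the planned placebo SD and mean (both 0.19). Nothing in the documents supports a shift of that size.

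Finally, the dropped dose's interim comparison is fully concurrent, and SAP 7.3 openly waives type I adjustment for the two-stage design. Both points are correct. But SAP 7.5.1 does not make the interim contrast the reported result, and waiving multiplicity control does not excuse a biased estimate and interval.

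**Conclusion.** The concern holds conditionally. If a dose is dropped and an unadapted Stage 2 is pooled under SAP 7.5.1, the dropped-dose contrast is biased by 0.6 times whatever placebo drift the covariates do not explain, in either direction. The 60% share and the bias formula follow from the SAP's sample sizes. The 5% to 19% range rests on equal variances and an assumed drift of 0 to 0.5 SD.

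The practical effect on the primary endpoint is likely to be modest. It is larger for the tubular-injury composite, and SAP 7.3 allows further enrolment specifically to support the secondary endpoints. The documents do not support a claim that the trial's main comparisons are compromised. The change is nevertheless cheap and improves on the stated model.

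**What to change.** In SAP 7.3, state how an unadapted Stage 2 is combined with Stage 1. In SAP 7.3 and 7.5.1 add, in substance:

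- When a dose has been dropped and the stages are pooled, stage (1/2) is a factor in the ANCOVA and MMRM.
- A sensitivity analysis compares the dropped dose only with placebo subjects randomised while that dose was open (Stage 1, about 20 v 20). This does not rely on drift being the same in both continuing arms.
- The dropped dose's Fisher's exact tests use the same concurrent placebo group, since those tests cannot adjust for stage.

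Stage should not be required as a further stratum in every CMH test. Three surgery types by three pump-time bands already make 9 strata; stage would make 18, with only 20 dropped-dose subjects.

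**Cost.** SAP wording and one model term. The dropped-dose standard error in the ANCOVA rises about 10% (0.292 v 0.265 SD), still below the 20 v 20 value of 0.316. Its Fisher's tests fall from 20 v 50 to 20 v 20 and lose power. The retained-dose contrast loses one degree of freedom. The stage term removes the bias fully only if drift is the same in both continuing arms, and it does not correct for unequal variances. If the sponsor no longer intends to drop a dose, deleting that branch resolves the point.

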## **7.4 Study Subjects**

### **7.4.1 Subject Disposition and Analysis Population**

Number of screened subjects, randomized subjects, study drug-treated subjects, and subjects receiving surgery will be provided overall and by treatment group. In addition, the number of randomized subjects completing the study and the reasons for discontinuation will be summarized overall and by treatment group.

Information on subject disposition will also be listed.

### **7.4.2 Protocol Deviations**

Major protocol deviations will be summarized overall and by treatment group for the randomized population. A listing will also be provided.

### **7.4.3 Study Populations**

The number of subjects in each study population will be summarized overall and by treatment group.

### **7.4.4 Demographic and Baseline Characteristics**

Demographic data and baseline characteristics, including a general medical history, will be summarized overall and by treatment group for the ITT and MITT populations.

AKI risk factors will be summarized by number of subjects meeting each risk factor, number of subjects meeting categorical and cumulative number of risk factors (eg, 0, 1-2,  $\geq 1$ ,  $\geq 2$ , and  $\geq 3$ ).

### **7.4.5 Study Drug Administration and Surgery**

Time of study drug administration before surgery, duration of infusion, duration of surgery, and time on pump will be summarized descriptively with mean and median by treatment group. Subjects with infusion interruption and subjects with infusion discontinuation will be summarized with number (n) and percent (%) of subjects by treatment group.

### **7.4.6 Prior and Concomitant Medication**

All medications taken by subjects from the time of Screening through Day 90 will be recorded. Medications will be coded for the therapeutic class and preferred term using the WHO Drug Dictionary (WHODD September 2021).

Subject incidence of prior medications, defined as medications taken prior to the study drug administration, will be summarized with number and % of subjects by therapeutic class and preferred term, overall and by treatment group, for the Safety and MITT population. Subject incidence of concomitant medications, defined as medications taken on/after the day of study drug administration, will be summarized similarly.

## 7.5 Efficacy Analysis

Primary endpoint will be analysed using both the ITT and MITT populations. All other efficacy endpoints will be analyzed using the MITT population.

Surgery type and time on pump may be used as covariates in ANCOVA or MMRM, or as stratification factor in Cochran-Mantel-Haenszel (CMH)  $\chi^2$  test. When used as stratification factor, time on pump will be trichotomized by the approximate tertile ( $\leq 90$ ,  $>90$  to  $120$ ,  $>120$  minutes) of the distribution in the MITT population. Other variables (eg, AKI risk factor and investigator site) may also be considered as covariates or stratification factors. The decision for including/excluding these variables as covariates or stratification factors will be based on the blinded review prior to any unblinded analysis.

### 7.5.1 Primary Efficacy Endpoint Analysis

The primary efficacy endpoint (geometric mean of the ratios of maximum PreOp over baseline in preconditioning biomarkers, Section 5.1) will be summarized using descriptive statistics (N, mean, median, standard deviation, minimum, and maximum) in the log scale and presented after the anti-log (exponential) transformation for each group separately.

An analysis of covariance (ANCOVA) model will be applied to the log-transformed primary efficacy endpoint. The model will include treatment group as main effect, and surgery type and time on-pump as covariates. Least squares mean (LSM) and the 95% confidence interval (CI) will be calculated for each treatment group and for the between active treatment and placebo difference. The LSM (95% CI) will be anti-log transformed and presented as the geometric LSM (GLSM) and 95% CI for each treatment group, and GLSM ratio (and 95% CIs) for each active treatment over placebo.

A sensitivity analysis will be carried out by the Cochran-Mantel-Haenszel (CMH)  $\chi^2$  test for the row mean score difference between active treatment and placebo stratified by the surgery type and time on pump. A modified ridit score will be used in the calculation of the CMH test statistic. As a supplementary analysis for the primary endpoint, each component of the composite endpoint

- $\frac{\text{max PreOp HO-1}}{\text{Baseline HO-1}}$
- $\frac{\text{max PreOp ferritin}}{\text{Baseline ferritin}}$
- $\frac{\text{max PreOp IL-10}}{\text{Baseline IL-10}}$

will be analyzed in the same way as for the primary efficacy endpoint.

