This is a Phase 2, multicenter, double-blind, randomized, placebo-controlled study to evaluate the effect of RBT-1 on preconditioning response biomarkers in subjects who are at risk for AKI following cardiac surgery. Eligible subjects will be randomized to receive a single dose of low-dose RBT-1 (45 mg SnPP/240 mg FeS), high-dose RBT-1 (90 mg SnPP/240 mg FeS), or placebo (normal saline) via intravenous (IV) infusion over a 120-minute period ≥ 24 but ≤ 48 hours prior to scheduled cardiac surgery.

All subjects will be assessed through Day 90 post-cardiac surgery. Subjects will be evaluated at Screening, 48 and/or 24 hours prior to surgery depending on the time of dosing, on Day 1 (day of surgery), and daily through Day 7 or Discharge if earlier, as well as on Days 30, 60, and 90, as described in the Event Schedule (see Section 5). Assessments include biomarkers of preconditioning response and tubular injury, urine output, incidence and severity of AKI, serum creatinine, days on ventilator, days in intensive care unit, hospital length of stay, readmission rate, and safety (physical examination, clinical laboratory assessment, vital signs, concomitant medications, and adverse events). Evaluations for MAKE (death, need for dialysis, and change in kidney function) and safety will be performed through Day 90, as described in the Event Schedule (see Section 5).

Number of Subjects to be Enrolled:

Approximately 126 subjects are planned to be enrolled and randomized 1:1:1 to low dose RBT-1, high-dose RBT-1, and placebo (n=42/group).

Inclusion Criteria:

Eligible subjects must meet all the following criteria:

1. Male or female subjects ≥ 18 years of age at Screening.
2. Able and willing to comply with all study procedures.
3. Stable kidney function per Investigator assessment and no known episodes of AKI during the preceding 4 weeks.
4. Scheduled to undergo non-emergent cardiac surgery requiring cardiopulmonary bypass (CPB), which must include one of the following:
 - CABG alone;
 - Combined CABG and cardiac valve(s) replacement or repair;
 - Cardiac valve(s) replacement or repair alone.
5. Female and male subjects of childbearing potential must agree to use 2 forms of contraception, with at least 1 being a barrier method, or abstain from sexual activity for 30 days following study drug administration.
6. Male subjects must agree not to donate or sell sperm for 30 days following study drug administration.

Exclusion Criteria:

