## 7 STATISTICAL METHODOLOGY

### 7.1 Determination of Sample Size

There will be three treatment groups; the two active (high dose [HD] 90/240 and low dose [LD] 45/240) groups will be compared to the control group. Using gatekeeping procedure for multiple comparisons and assuming the primary endpoint log composite score derived from this study is comparable to the score derived from the REN-003 and REN-001A studies (HD: mean  $\pm$  SD 1.30 $\pm$ 0.56, LD: 1.07 $\pm$ 0.52, and placebo: 0.19 $\pm$ 0.19), a sample size of 10 subjects per group will provide >80% power for the between group comparisons with two-sided  $\alpha=0.05$  significance level.

Using the REN-003 Study “FDA Safety Summary-1 Updated Feb2020.docx” non-surgical healthy volunteer and CKD patient data mixture, the secondary endpoint log composite score is estimated as 0.41  $\pm$  0.51. Thus, with the sample size of 10, 20, and 30 subjects per group, the study will have 40%, 69%, and 86% power, respectively, to detect a between active group and placebo group difference in the mean log composite score of 0.4, or a between group ratio of 1.5 in the composite score.

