## 7.2 General Statistical Considerations

Continuous variables will be summarized overall and by treatment group using descriptive statistics (e.g., N, mean, median, standard deviation [SD], Q1, Q3, minimum and maximum), while categorical variables will be summarized with number and proportion of subjects for each category.

In addition to the data summary and between group comparison, all data will be presented in the data listings with subject ID, treatment group, and other pertinent information.

For serum creatinine and eGFR, missing or aberrant central lab test results will be replaced by the local lab test results if available, or if not available, by linear interpolation by the two data points before and after the missing data point (not applicable for Day 7, Day 30, 60, and 90 tests). If Visit 1a is missing, and the corresponding local lab is not available, it will be imputed with the screening local lab result. Day 7 (Visit 8) lab test is collected on the nominal Day 7. If patients are discharged early, their discharge values from Days 4, 5, or 6 will be reported as Day 7 values. If Day 7 is missing, and the corresponding local lab result is not available, it will be imputed with the last value collected Day 3 through Day 6. All imputations will be documented and signed off prior to the database lock for analysis. Biomarker values below the limit of quantification (LLOQ) will be replaced by the LLOQ value divided by 2. Biomarker values above the limit of quantification (ULOQ) will be replaced by the ULOQ value.

Unless specified otherwise, all between group comparisons and confidence intervals will use 2-sided  $\alpha=0.05$  significance level.

Statistical analyses will be performed using SAS version 9.4 or higher.

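### The primary ANCOVA specifies no arm-specific variance although the SAP plans on log-scale SDs of 0.56, 0.52 and 0.19, so if those SDs recur the per-arm 95% CIs misstate precision while the contrasts with placebo stay conservative

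*SAP*

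**What the plan says.** For the primary composite, SAP 7.5.1 says "An analysis of covariance (ANCOVA) model will be applied to the log-transformed primary efficacy endpoint". The model has treatment as the main effect, with surgery type and time on pump as covariates. From it, "Least squares mean (LSM) and the 95% confidence interval (CI) will be calculated for each treatment group", and likewise for each active-minus-placebo difference. These are back-transformed to geometric least squares means (GLSMs) and GLSM ratios. The section mentions no arm-specific residual variance, adjusted degrees of freedom or robust standard error. By contrast, SAP 7.5.3.2 does specify a covariance structure and a degrees-of-freedom method for the repeated-measures creatinine model.

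The SAP 7.1 sample size rests on "assuming the primary endpoint log composite score derived from this study is comparable to the score derived from the REN-003 and REN-001A studies". The means and SDs given there are HD 1.30 (0.56), LD 1.07 (0.52) and placebo 0.19 (0.19). The protocol synopsis has subjects "randomized 1:1:1 to low dose RBT-1, high-dose RBT-1, and placebo (n=42/group").

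**The concern.** An ANCOVA with one residual variance gives all three arms the same error SD. On the SAP's planning figures the HD variance is 0.56² / 0.19² = 8.7 times the placebo variance. A common SD would then be too small for the active arms and much too large for placebo. With equal arm sizes, all three arm means would be reported with about the same precision, while the descriptive SDs in the same section would differ about threefold.

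What is at stake is the accuracy of intervals that the SAP commits to report for its primary endpoint. In a two-dose Phase 2 trial, the per-arm intervals describe the response to each dose and may be used in planning later work.

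**Working it through.** **Inputs.** Means and SDs: SAP 7.1, as above. Two-sided alpha of 0.05: SAP 7.2. Arm size of 42: protocol synopsis. Model: SAP 7.5.1, with two degrees of freedom assumed for surgery type (three types) and one for time on pump. Residual df are then 126 − 6 = 120 and the critical t is 1.980.

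**The plan's own figure first.** SAP 7.1 says "a sample size of 10 subjects per group will provide >80% power for the between group comparisons". With 10 per group and the pairwise SD √((s₁² + s₀²)/2):
- HD vs placebo: difference 1.11, SD 0.418, power 99.99% (t test) or 99.97% (Welch).
- LD vs placebo: difference 0.88, SD 0.391, power 99.7% (t test) or 99.5% (Welch).

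The stated power of more than 80% is reproduced. With the three-arm pooled SD derived below, power at 10 per group is still 99.95% for HD and 98.6% for LD.

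**Pooled SD at equal arm sizes.** √((0.56² + 0.52² + 0.19²)/3) = √(0.6201/3) = 0.455.

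**Coverage.** Let r be the model's standard error divided by the true one. For an arm mean, r = 0.4546/sᵢ. For a contrast, r = √2 × 0.4546/√(s_active² + s_placebo²). Actual coverage of a nominal 95% CI is about 2Φ(1.980 r) − 1. The simulated column comes from 10,000 runs with normal errors, and with surgery type and pump time in the model but having no true effect.

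| Quantity (42 per arm) | r | Coverage, formula | Coverage, simulated |
|---|---|---|---|
| HD mean | 0.81 | 89.2% | 89.1% |
| LD mean | 0.87 | 91.7% | 91.8% |
| Placebo mean | 2.39 | about 100% | 100% |
| HD − placebo | 1.09 | 96.9% | 96.7% |
| LD − placebo | 1.16 | 97.9% | 97.5% |

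The contrasts are conservative because the common SD also carries the variance of the other active arm: 0.455, against the pairwise 0.418 and 0.391. At equal arm sizes r does not depend on n, so a larger trial does not cure the problem.

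**On the reported scale**, with the planning means as point estimates:

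| Arm | Log half-width, pooled | Log half-width, own SD | GLSM CI, pooled | GLSM CI, own SD |
|---|---|---|---|---|
| HD | 0.139 | 0.175 | 3.19–4.22 | 3.08–4.37 |
| LD | 0.139 | 0.162 | 2.54–3.35 | 2.48–3.43 |
| Placebo | 0.139 | 0.059 | 1.05–1.39 | 1.14–1.28 |

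**Sensitivity to the SDs.** As an illustration, double the placebo SD to 0.38 and leave the others unchanged. The pooled SD is √((0.3136 + 0.2704 + 0.1444)/3) = 0.493, and r is 0.88 (HD), 0.95 (LD) and 1.30 (placebo). Coverage is then about 92%, 94% and 99%. With three equal SDs every r is 1 and nothing is wrong.

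**Hypothetical unequal arms.** SAP 7.3 mentions about 20 per group in Stage 1 and, if a dose is dropped, 30 more in each remaining group. Pooling the stages would give 20/50/50. With HD dropped, the pooled variance is (19 × 0.3136 + 49 × 0.2704 + 49 × 0.0361)/117 = 0.179, so the SD is 0.423. The model SE for HD − placebo is 0.423 × √(1/20 + 1/50) = 0.112, against a true √(0.3136/20 + 0.0361/50) = 0.128. Then r = 0.87 and coverage is about 92% (also about 92% simulated). With LD dropped, LD − placebo coverage is about 94%. The retained dose's contrast stays at about 96% in both cases.

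**The case against.** The strongest case against the point is that the confirmatory comparisons are not harmed. The gatekeeping sequence in SAP 7.3 tests HD and then LD against placebo, and at 1:1:1 both CIs err on the wide side. That stands, and it limits the point to reported precision. A reader might infer inflated type I error, but the documents do not support that. If the drug has no effect on the distribution, the variances are equal and the pooled model is correct. If the planning SDs hold, the planned contrasts over-cover.

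A reader might also take the SDs as what the SAP expects to see. They are a sample-size assumption from earlier studies, without the arm sizes behind them. SAP 7.3 itself says that the composite has not been measured before in cardiac surgery patients given this drug. The size of the effect is therefore conditional.

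The 20/50/50 case is remote. The protocol plans three equal arms, SAP 7.3 calls its adaptation rule guidance only, and the stages are analysed separately if Stage 2 is adapted on AKI risk. Nor is an HD-versus-LD comparison planned, so coverage for it is not at issue.

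Finally, the SAP reports each arm's own log-scale SD and adds a stratified CMH test with modified ridit scores. Readers would see unequal spread, and the CMH test does not use the pooled variance. Neither one corrects a GLSM or ratio CI, so this part does not answer the point.

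**Conclusion.** The point holds as a matter of reported precision. If the SAP 7.1 SDs recur at 42 per arm, the HD and LD mean CIs use standard errors 19% and 13% too small, and the placebo CI is wider than it should be by a factor of 2.4. The two ratio CIs are valid but wider than necessary. Neither the alpha of the planned tests nor the likely primary conclusion is at risk. Under-coverage of a contrast arises only for a dropped dose, and only if the stages are pooled.

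The conclusion rests on two assumptions: that ANCOVA without further specification means a single residual variance, which the SAP does not say outright, and that the spread in surgical patients resembles the planning SDs. It is worth correcting before unblinding because the correction is cheap, but it is not a fatal flaw.

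**What to change.** In SAP 7.5.1, keep the model for the primary composite and add that the residual variance is estimated separately for each treatment group, with Satterthwaite or Kenward-Roger degrees of freedom. In SAS this can be done with a mixed-model procedure using REPEATED / GROUP=treatment. Heteroscedasticity-consistent standard errors are an alternative. In the simulation at 42 per arm, the HC3 form gave coverage of 94.9% (HD), 95.1% (LD), 96.5% (placebo), and 95.4% for both contrasts.

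On the planning SDs the contrasts also gain precision: the HD-placebo SE falls from 0.099 to 0.091 and the LD-placebo SE from 0.099 to 0.085.

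Extending the change to the three component ratios and the tubular-injury composite is optional and for consistency only. SAP 7.1 gives no SDs for the components and a single SD of 0.51 for the tubular-injury composite, so no unequal variance is shown there.

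The cost is one sentence, one code option and slightly fewer degrees of freedom. If the variances prove equal, little is lost.
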